## CONFIDENTIAL

207660

Population	Definition / Criteria	Analyses Evaluated
	treatment actually given.	
Safety4	
 
This population consists of all participants in Safety1 population, who receive study treatment four times.
 
The participants will be analyzed based on the treatment actually given.
 
	
 
Safety
 

**NOTES :**

- Please refer to [Appendix 12](#): List of Data Displays which details the population to be used for each displays being generated.

**4.1. Protocol Deviations**

Important protocol deviations (including deviations related to study inclusion/exclusion criteria, conduct of the trial, patient management or patient assessment) will be summarised and listed.

Protocol deviations will be tracked by the study team throughout the conduct of the study in accordance with the Protocol Deviation Management Plan.

- Data will be reviewed prior to unblinding and freezing the database to ensure all important deviations are captured and categorised on the protocol deviations dataset.
- This dataset will be the basis for the summaries and listings of protocol deviations.

A separate listing of all inclusion/exclusion criteria deviations will also be provided. This listing will be based on data as recorded on the inclusion/exclusion page of the eCRF.

**5. CONSIDERATIONS FOR DATA ANALYSES AND DATA HANDLING CONVENTIONS****5.1. Study Treatment & Sub-group Display Descriptors**

Treatment Group Descriptions			
RandAll NG		Data Displays for Reporting	
Code	Description	Description	Order in TLF
A	GSK1358820 240U	GSK1358820 240U	1
B	GSK1358820 400U	GSK1358820 400U	2

Treatment comparisons will be displayed as follows using the descriptors as specified:

- GSK1358820 400U vs GSK1358820 240U

CONFIDENTIAL

207660

## 5.2. Baseline Definitions

For all endpoints (except as noted in baseline definitions) the baseline value will be the latest pre-dose assessment with a non-missing value, including those from unscheduled visits. If time is not collected, Day 1 assessments are assumed to be taken prior to first dose and used as baseline. These baseline values will be used for all analyses in both Blind Phase and Open Label Phase.

Unless otherwise stated, if baseline data is missing no derivation will be performed and baseline will be set to missing.

## 5.3. Multicentre Studies

No data will be analysed by center.

## 5.4. Examination of Covariates, Other Strata and Subgroups

### 5.4.1. Covariates and Other Strata

The list of covariates and other strata may be used in descriptive summaries and statistical analyses, some of which may also be used for subgroup analyses. Additional covariates and other strata of clinical interest may also be considered.

Category	Details
Strata	Baseline MAS value of the elbow (3 or 4)

### 5.4.2. Examination of Subgroups

The list of subgroups may be used in descriptive summaries and statistical analyses. Additional subgroups of clinical interest may also be considered.

- If the percentage of participants is small within a particular subgroup, then the subgroup categories may be refined prior to unblinding the trial.
- If the category cannot be refined further, then descriptive rather than statistical comparisons may be performed for the particular subgroup.

Subgroup	Categories
Baseline MAS value of the elbow	3 or 4
Baseline Rehabilitation	
Task-specific practice	Yes, or No
Muscle strengthening exercise	The subgroup analyses will be conducted by each rehabilitation use.
Stretching/Range of motion exercise	
Splinting/Orthoses	
Taping	
Positioning aids	

## 5.5. Multiple Comparisons and Multiplicity

No multiplicity adjustment is considered in this study because no statistical hypothesis will be tested.

## 5.6. Other Considerations for Data Analyses and Data Handling Conventions

Other considerations for data analyses and data handling conventions are outlined in the appendices:

Section	Component
Section 10.3	Appendix 3: Assessment Windows
Section 10.4	Appendix 4: Study Phases and Treatment Emergent Adverse Events
Section 10.5	Appendix 5: Data Display Standards & Handling Conventions
Section 10.6	Appendix 6: Derived and Transformed Data
Section 10.7	Appendix 7: Reporting Standards for Missing Data
Section 10.8	Appendix 8: Values of Potential Clinical Importance

## 6. STUDY POPULATION ANALYSES

### 6.1. Overview of Planned Study Population Analyses

The study population analyses will be based on the Screened, Enrolled and ITT populations, unless otherwise specified.

Study population analyses including analyses of participant's disposition, protocol deviations, demographic and baseline characteristics, prior and concomitant medications, and rehabilitations will be based on GSK Core Data Standards. Details of the planned displays are presented in [Appendix 12: List of Data Displays](#).

### 6.2. Participant Disposition and Population

The number and percentage of those participants below will be presented by treatment group and total.

- Participants who completed the Week 24 and who withdrew early from study by Week 24 (including the reasons for early withdrawal)
- Participants who completed the study and who withdrew early from study (including the reasons for early withdrawal)
- Participants who passed screening and who failed screening (including the reasons for screen failure)
- Participants at each centre
- Participants included in each population defined in the Section 4.

**CONFIDENTIAL**

207660

These items below will be listed.

- The reasons for early withdrawal and screen failure.
- Participants who were rescreened.
- Participants for whom the treatment blind was broken.
- Planned and actual treatments
- Participants excluded from any population defined in the Section 4.

**6.3. Protocol Deviation**

The number and percentage of participants with important protocol deviation will be presented by treatment group. This summary will not include subcategories

Important protocol deviations and participants with inclusion/exclusion criteria deviation will be listed.

**6.4. Demographic and Baseline Characteristics**

These parameters as below will be summarized by treatment group and total.

- Demographic data (age, sex, ethnicity, weight, height, body mass index(BMI), race and racial combinations)
- Baseline Efficacy Parameter
  - Continuous variable
    - Modified Ashworth Scales in finger, thumb, wrist and elbow
    - Numeric Rating Scale for pain in elbow
    - Disability Assessment Scale (Main Assessment Parameter)
    - Disability Assessment Scale (Hygiene, Pain, Dressing and Limb posture)
  - Categorical variable
    - Baseline MAS score of the elbow (3 or 4, original values) as randomization strata
    - The selected item as a Main Assessment Parameter of DAS out of the 4 items
      - Hygiene
      - Pain
      - Dressing
      - Limb posture

CONFIDENTIAL

207660

## 6.5. Prior and Concomitant Medications

All medication used in this study will be coded according to drug name as defined in the GSK Drug Dictionary. The relationship between the ATC level 1 and ingredient will be summarized for the all prior and concomitant medications, respectively.

## 6.6. Rehabilitation

- Screening

The number and percentage of Rehabilitations will be presented.

- Treatment phase

The category and frequency of Rehabilitations will be collected on eCRF. The number and percentage of each Rehabilitation will be presented in Blind Phase. The category and frequency of Rehabilitations in all treatment phase will be listed.

- Category and Frequency

The categories of Rehabilitation are as below:

- Task-specific practice
- Muscle strengthening exercise
- Stretching/Range of motion exercise
- Splinting/Orthoses
- Taping
- Positioning aids

The category of frequency which will be collected on CRF is defined as below:

- No practice
- > 0 and ≤ 8 days per month
- > 8 and ≤ 16 days per month
- > 16 and ≤ 24 days per month
- > 24 days per month

## 6.7. Other Surgical Procedure

The other surgical procedure except for Rehabilitation will be listed by treatment group.

**6.8. Actual dose**

The dosage in each muscle and joint to which more than 0 unit of GSK1358820 is administered will be summarized by treatment group and treatment cycle. The Relationship between Muscle Region and Joint is shown below in each treatment phase.

- Muscle Region

If a muscle region of a participant is not treated, the muscle will not be included when calculating the summary statistics.

Example	Dosage of Biceps brachii (unit)	Mean
Subject PPD	0	$(40 + 80 + 120) / 3 = 80$ units
Subject	40	
Subject	80	
Subject	120	

- Joint

If no muscle region of a Joint of a Participant is treated, the corresponding joint will not be included when calculating the summary statistics.

Example	Muscle Region	Dosage of each Muscle (unit)	Dosage of Elbow (unit)	Mean
Subject PPD	Biceps brachii	0	0	$(100 + 110 + 180) / 3 = 130$ units
	Brachialis	0		
	Brachioradialis	0		
Subject	Biceps brachii	0	100	
	Brachialis	20		
	Brachioradialis	80		
Subject	Biceps brachii	10	110	
	Brachialis	40		
	Brachioradialis	60		
Subject	Biceps brachii	40	180	
	Brachialis	60		
	Brachioradialis	80		

- Blind Phase

Joint	Each muscle region
Elbow	Biceps brachii
	Brachialis
	Brachioradialis
Wrist	Flexor carpi radialis
	Flexor carpi ulnaris

Joint	Each muscle region
Finger	Flexor digitorum profundus
	Flexor digitorum superficialis
Thumb	Flexor pollicis longus
	Adductor pollicis

- Open Label Phase

Joint	Each muscle region
Elbow	Biceps brachii
	Brachialis
	Brachioradialis
Wrist	Flexor carpi radialis
	Flexor carpi ulnaris
Finger	Flexor digitorum profundus
	Flexor digitorum superficialis
	Lumbricales interossei
Thumb	Flexor pollicis longus
	Adductor pollicis
	Opponens
Forearms	Pronator teres
	Pronator quadratus
Shoulder	Teres major
	Latissimus dorsi
	Pectoralis major
	Subscapularis

## 7. EFFICACY ANALYSES

### 7.1. Primary Efficacy Analyses

#### 7.1.1. Endpoint / Variables

The primary endpoint is the responder rate of MAS score in the elbow flexors at Week 6 of the initial dose.

#### 7.1.2. Summary Measure

The summary measure is the difference in the responder rate of MAS score in the elbow flexors.

## CONFIDENTIAL

207660

**7.1.3. Population of Interest**

The primary efficacy analyses will be based on the Intent-To-Treat 1 population, unless otherwise specified.

**7.1.4. Strategy for Intercurrent (Post-Randomization) Events**

Intercurrent event: early withdrawal from study

Strategy : if MAS score is missing because of an early withdrawal from the study, the participant will be regarded as a non-responder.

**7.1.5. Statistical Analyses / Methods**

Details of the planned displays are provided in [Appendix 12](#): List of Data Displays and will be based on GSK data standards and statistical principles.

Unless otherwise specified, endpoints / variables defined in Section [7.1.1](#) will be summarised using descriptive statistics and listed.

**7.1.5.1. Statistical Methodology Specification**

Endpoint / Variables

 
• Responder Rate of MAS in the elbow flexors at Week 6 of the initial dose
 

Model Specification

 
• To summarize the primary endpoint without statistical model 
 
○ The primary endpoint will be calculated as the proportion of participants whose MAS score decreased by at least 1 level from the baseline in the ITT1 population.
 
○ The intergroup difference in the responder rate and its 95% confidence interval (Wald-type) will be computed.
 
 
 

Data Convention

 
• The MAS scores, 0, 1, 1+, 2, 3 and 4 will be encoded to 0, 1, 2, 3, 4 and 5, respectively, for the analyses.
 

Definition of Responder and Responder rate

“Responder” is defined as a participant whose MAS score decrease by at least 1 level from the baseline.
 
Responder Rate will be calculated as below.
 
Responder Rate (%) = (Number of Responders) / (Number of participants in ITT1 population) x 100
 
 
• If MAS score of a given participant is missing at Week 6, then this participant will be regarded as a non-responder.
 

Model Results Presentation

 
• The difference in the responder rate (400 units – 240 units) and its associated 95% CI will be presented.
 

Subgroup Analyses (Rehabilitation)

 
Subgroup analyses will be performed by baseline rehabilitation in the Section 5.4.
 
The difference (400 units – 240 units) and its 95% CI will be presented.
 

Subgroup Analyses (baseline MAS score)

 
Subgroup analyses will be performed by baseline MAS score of the elbow (3 or 4) used as randomization strata.
 
The difference (400 units – 240 units) and its 95% CI will be presented.
 

Supportive Analyses

 
The difference in the responder rate will be estimated using Mantel-Haenszel method to consider a stratification factor, that is baseline MAS score of the elbow (3 or 4).
 
Mantel-Haenszel rate difference (400 units – 240 units) and its 95% CI will be calculated.
 

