### 2.3. Study Design

Overview of Study Design and Key Features	

The diagram illustrates the study design timeline. It begins with a 'Screening' phase. This is followed by a 'Double-blind treatment' phase lasting 12 weeks, labeled as 'Part 1'. In this phase, participants are randomized to receive either 'BOTOX 400 U' or 'BOTOX 240 U + Placebo'. After the double-blind phase, the study enters an 'Open-label treatment' phase lasting 36 weeks, which is divided into three parts: 'Part 2', 'Part 3', and 'Part 4'. All participants in the open-label phase receive 'BOTOX 400 U'. Arrows labeled 'dose' indicate the timing of each injection.
	
Design Features	
This study includes a Screening Phase, Blind Phase, and Open-label Phase. The study design of each treatment phase is shown below.
 
 
Blind Phase: Multicenter, randomized, double-blind, placebo-controlled, parallel-group comparison design
 
Open-Label Phase: Multicenter, uncontrolled, open-label design
 

Dosing	
 
In the Blind Phase, participants will be randomly assigned 1:1 to either the 400 or the 240-unit group.
 
In the 400-unit group, 240 units of the product will be injected into the
 

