## CONFIDENTIAL

207660

Overview of Study Design and Key Features	
	
muscles that act on the finger (including thumb flexors) and wrist flexors, and 160 units into the muscles that act on the elbow flexors. A total of 400 units of the product will be injected.
 
 
• In the 240-unit group, 240 units of the product will be injected into the muscles that act on the finger (including thumb flexors) and wrist flexors. Placebo will be injected into the muscles that act on the elbow flexors. A total of 240 units of the product will be injected.
 
• In the Open-label phase, a total of 400 units will be injected in both groups. 
 
• The product can be injected up to 3 times after completion of Part 1 in the blind phase. Participants whom the investigator considers as eligible for the injections will be treated. The next injections cannot be performed until the eligibility of the participant has been confirmed by the investigator.
 
• The muscle to be injected and the dose will be decided by the investigator based on the patient's symptoms, and a total dose of 400 units of the product will be injected in a divided dose. For the muscles that the investigator considers as unnecessary to be treated, an injection may be skipped. The involving muscle and the dose do not have to be same each time always.
 
 
 

Treatment Assignment	
 
• Number of participants (randomized participants): 120 (60 per group)
 
• GSK RandAll NG will be used to generate the randomization schedule.
 
• The randomization will be stratified by the MAS score (3 or 4) in the elbow flexors at Day1
 

Interim Analysis	
 
• Interim analysis is planned in this study as described in 3.1.
 

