##### 7.2.5.1. Statistical Methodology Specification

Secondary Efficacy Analysis
Endpoint / Variables

 
Change from baseline in MAS in each joint and DAS (Main Assessment Parameter) scores
 

Model Specification

 
The endpoint will be analyzed using a mixed model for repeated measures (MMRM)
 
Terms fitted in the MMRM will include the items below as fixed effects. 
 
Categorical effect 
 
Treatment
 
Visit
 
Treatment-by-visit interaction
 
 
 
Continuous effect 
 
Baseline value in MAS of each joint or in DAS (Main Assessment Parameter)
 
Baseline-by-visit interaction
 
 
 
 
 
An unstructured variance structure will be used to model the within-participant errors, shared across treatments.
 
The empirical sandwich estimator will be used to estimate the standard errors.
 

Model Checking & Diagnostics

 
If the model will not converge with unstructured variance, AR(1) variance structure can be
 

CONFIDENTIAL

207660

Secondary Efficacy Analysis
used.
Model Results Presentation

 
Adjusted means (least square means) and corresponding standard errors of means will be presented for each treatment by visit, together with estimated treatment differences (400 units – 240 units) and the corresponding 95% CI.
 

Data included in Model

 
The dataset including only data until week 12 after the first treatment will be used.
 

Secondary Efficacy Analysis
Endpoint / Variables

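### The primary responder difference and the four non-elbow MMRMs leave out the randomisation stratum, at a small and conservative cost; the subgroup rows name no interval method

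*SAP*

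**What the plan says.** Section numbers are those of the amended plan.

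- **Design (2.3).** 120 participants, 60 per group, allocated 1:1. "The randomization will be stratified by the MAS score (3 or 4) in the elbow flexors at Day1".
- **Primary analysis (7.1.5.1).** The Week 6 elbow responder rates are compared without a model: "The intergroup difference in the responder rate and its 95% confidence interval (Wald-type) will be computed".
- **Supportive analysis (7.1.5.1).** "The difference in the responder rate will be estimated using Mantel-Haenszel method to consider a stratification factor", namely baseline elbow MAS, with a 95% interval. Section 7.2.5.1 carries this estimator to the responder rates of all joints and keeps the elbow stratum as the factor in each. Table 2.04 in Section 10.12.5.1 calls for it.
- **MMRMs (7.2.5.1).** The terms are treatment, visit, their interaction, the outcome's own baseline and baseline by visit, with sandwich standard errors. Only the elbow model carries the stratifying variable, as its own baseline.
- **Subgroups (7.1.5.1).** For the rehabilitation rows and the MAS 3/4 rows: "The difference (400 units – 240 units) and its 95% CI will be presented". No interval method is named.
- **Small subgroups (5.4.2).** Categories may be refined before unblinding, or the comparison may be descriptive only. Neither is required, and no size threshold is set.
- **Testing (2.4, 5.5).** No hypothesis is tested and there is no multiplicity adjustment.

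**The concern.** The stratifying variable is the baseline of the scale on which primary response is scored, so it may well be prognostic. Stratified randomisation balances it between arms. An unstratified variance still counts the between-stratum variation that this balance removes, so the interval can be wider than the design requires. The plan already holds the matching estimator but ranks it second.

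The secondary analyses are also inconsistent. For finger, wrist and thumb, the supportive responder estimate uses the elbow stratum while the MMRM of the same scores does not. DAS has no stratified analysis at all.

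The subgroup issue runs the other way. A Wald interval is too short in small cells, and six rehabilitation items split Yes/No could produce some. With no test planned, the estimates and their intervals carry the results. The stake is therefore precision and coverage, not a type I error decision.

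**Working it through.** The SAP gives no responder rates, stratum shares or subgroup sizes. Everything below except 60 per arm and 1:1 allocation is an assumption. For the same reason the sample size of 120 cannot be reproduced from this document.

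**1. Primary interval, 60 per arm**

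Unstratified variance: [p₁(1−p₁) + p₀(1−p₀)]/60.

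Stratified variance, Mantel-Haenszel weights, strata balanced 50:50 (30 per arm in each): 0.25 × Σ[p₁ₛ(1−p₁ₛ) + p₀ₛ(1−p₀ₛ)]/30.

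Half-width: 1.96 × √variance.

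*20-point gap: 400 U 0.7/0.5, 240 U 0.4/0.2; overall 0.6 and 0.3*
- Unstratified: (0.24 + 0.21)/60 = 0.00750, half-width 16.97 points.
- Stratified: 0.25 × (0.21 + 0.24 + 0.25 + 0.16)/30 = 0.00717, half-width 16.59 points.
- Variance ratio 1.047; width ratio √1.047 = 1.023; the unstratified interval covers 2Φ(1.96 × 1.023) − 1 = 95.5%.

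*30-point gap: 400 U 0.8/0.5, 240 U 0.5/0.2; overall 0.65 and 0.35*
- Unstratified: (0.2275 + 0.2275)/60 = 0.00758, half-width 17.07 points.
- Stratified: 0.25 × (0.16 + 0.25 + 0.25 + 0.16)/30 = 0.00683, half-width 16.20 points.
- Variance ratio 1.110; width ratio 1.053; coverage 96.1%.

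*Sensitivity.* With overall rates of 75% and 45% and between 10% and 50% of participants in the MAS 4 stratum, the unstratified interval is wider by:

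| Gap between strata | Excess width |
|---|---|
| 0 points | 0% |
| 20 points | 0.8 to 2.4% |
| 30 points | 1.9 to 5.6% |
| 40 points | 3.5 to 10.7% |

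**2. Wald at full size.** Exact binomial enumeration at 60 per arm gives coverage of 0.945 to 0.948 over seven rate pairs (0.945 at 0.6 against 0.3).

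**3. Non-elbow MMRMs.** If r is the partial correlation of the elbow stratum with the outcome, given its own baseline, the width ratio is about 1/√(1−r²): 1.005 at r = 0.1, 1.021 at r = 0.2 and 1.048 at r = 0.3.

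**4. Subgroup rows, if they use Wald (exact enumeration)**

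| Per arm | Rates | Wald | Newcombe |
|---|---|---|---|
| 15 | 0.6, 0.3 | 0.913 | 0.946 |
| 10 | 0.6, 0.3 | 0.934 | 0.936 |
| 10 | 0.7, 0.2 | 0.894 | 0.957 |
| 8 | 0.6, 0.2 | 0.880 | 0.918 |
| 5 | 0.8, 0.2 | 0.877 | 0.925 |

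In the last row both arms must be all or none for a zero-width interval: (0.8⁵ + 0.2⁵)² = 0.328² = 0.108, a 10.8% chance. Coverage does not fall smoothly with size. Over the seven rate pairs it is 0.916 to 0.936 at 6 per arm and 0.865 to 0.884 at 5. At 30 per arm it is 0.920 to 0.943.

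**The case against.** The strongest reply is that the stratified estimate will be produced anyway. It is prespecified with its interval for the primary endpoint and for every joint, and the primary difference is also shown within each stratum. Under 1:1 allocation the unstratified difference estimates the marginal effect without bias, so the dispute is largely over which result leads. The possible loss is under one point of half-width in the worked cases (0.4 and 0.9) and errs on the safe side. The SAP sets no success threshold that it could move. Nor is the stratified interval perfect: in simulation at 75% against 45%, with stratum gaps of 0 to 40 points, it covered 94.2 to 94.6%, against 94.7 to 96.8% for the unstratified one. All of this stands and limits the weight of the point. It does not explain why the main interval should differ from the randomisation when the matching one is already planned, and it does not reach the MMRMs, which have no stratified counterpart.

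A reader might infer that the plan ignores the stratum altogether. It does not; Sections 7.1.5.1 and 7.2.5.1 and Table 2.04 rule that out. A reader might also take it as settled that subgroup intervals are Wald. That is only an inference: Wald is the one method named in the table for an unstratified difference. Section 5.4.2 also offers a way out for sparse subgroups, though it is optional and has no threshold.

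**Conclusion.** The point holds as a modest matter of efficiency and specification. The main responder interval and the DAS, finger, wrist and thumb MMRMs omit the factor used in randomisation.

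The cost to the primary interval depends on how prognostic elbow MAS 3 against 4 is, which the SAP does not say. It is nil if the strata do not differ and roughly 1 to 5% of width for a 20 to 30 point gap, reaching 5.6% at one corner of the grid. For the MMRMs it is about 0.5 to 5% for partial correlations of 0.1 to 0.3. In both cases the error is conservative, so it would be wrong to infer bias or an invalid primary result.

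The subgroup rows are under-specified. Under-coverage there depends on two unknowns, the method actually used and the cell sizes. It is a few points in most cases at 10 to 30 per arm and becomes serious at about 5 per arm.

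**What to change.** 1. In Section 7.1.5.1, make the Mantel-Haenszel difference by elbow MAS 3/4, with its 95% interval, the main estimate, and keep the unstratified Wald difference as supportive. If the protocol fixes the unstratified difference as primary, list the switch in Section 2.1, which at present declares only a change to an exploratory MAS endpoint.
2. In Section 7.2.5.1, add the elbow stratum as a fixed effect to the DAS, finger, wrist and thumb MMRMs. The elbow model needs no change.
3. In the subgroup rows, name a Newcombe or Miettinen-Nurminen interval, and give Section 5.4.2 a minimum cell size below which only counts and rates are shown.

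The cost is SAP wording, one extra term in four models and a different interval routine for the subgroup rows. The Mantel-Haenszel estimate is already a planned display and no new data are needed. The changes should be fixed before the unblinding for the interim analysis.
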